5.3.2 Randomized Portion

All adverse events and toxicities will be graded and reported according to the revised NCI Common Terminology Criteria for Adverse Events (CTCAE) version 4.0. The CTCAE version 4.0 is located on the CTEP website at

http://ctep.cancer.gov/protocolDevelopment/electronic_applications/ctc.htm. See

Appendix VII for Adverse Event (AE) definitions and grading scale information.

If multiple toxicities are seen, the presence of a DLT should be based on the most severe toxicity experienced. Any patient who achieves a DLT will be taken off of the investigational medication immediately, but will still be evaluable.

Concerning Toxicity

1. Any **asymptomatic grade 3 or 4 hypoglycemia** as defined by CTCAE version 4.0.
2. Any **non-hematologic grade 3 or greater toxicity** (including neurologic toxicity) that is associated with a blood glucose level ≤ 80 mg/dl and is resolved with "low blood sugar intervention" (e.g. a return of blood glucose level to ≥ 80 mg/dl).

Serious Toxicity

1. Any **grade 5 toxicity** that is deemed by the investigator to be **at least possibly attributable to the investigational medication**.
2. Any **symptomatic grade 3 or 4 hypoglycemia** that is associated with a **non-hematologic grade 3 or greater toxicity** that is not resolved with “low blood sugar intervention” (e.g. does not return to blood glucose level of ≥ 80 mg/dl) that is deemed by the investigator to be **at least possibly attributable to the investigational medication**.

Investigational medication will be discontinued for any patient that meets the criteria for a “concerning toxicity” or “serious toxicity”. These patients will still be evaluable. All other patients currently on treatment at the time may continue with their current investigational medication without interruption.

5.4 Safety and efficacy (blood glucose monitoring)

5.4.1 Pilot Portion

All patients will be provided with a medication/blood glucose log, a blood glucose monitor, and taught to perform self fingerstick glucose draws (see Appendices II-VI). The first blood glucose draw will be done by a nurse or research team member on the visit 5-9 days prior to SRS and the initial value will be recorded in the blood glucose log. Starting at the initiation of glyburide and for at least the first week after SRS, the patient will take and record blood glucose levels 4 times a day (in the morning before breakfast [fasting], before lunch, before dinner, and before bed). After one week post SRS, if the patient does not experience a dose limiting toxicity (DLT, as defined in section 5.3.1), he/she will be instructed to obtain blood glucose levels once a day (in the morning before breakfast [fasting]) until the discontinuation of glyburide. If the patient does experience a DLT then he/she must discontinue glyburide (as per section 5.3.1) and will not have to continue checking their blood glucose levels.

If the patient is symptomatic and this is thought to be attributable to hypoglycemia, he/she should check a fingerstick glucose level and begin “low blood sugar intervention” as described in **Section 5.4.1.1** (also see Appendix IV). If fingerstick glucose levels reach ≤ 80 mg/dl (symptomatic or asymptomatic), the patient should begin “low blood sugar intervention”. If “low blood sugar intervention” does not cause the blood sugar to rise above 80 mg/dl, or if symptoms persist, the patient will be instructed to contact the study team and/or call 911 for emergency services.

5.4.1.1 “Low Blood Sugar Intervention”:

Procedures:

1. Take 15 grams of carbohydrate:
 - a. 3 or 4 glucose tablets or
 - b. 4 oz (1/2 cup) of fruit juice or
 - c. 6 oz regular soda (about 1/2 can)
2. Rest and wait 15 minutes
3. Recheck blood sugar

4. Repeat Steps 1-3 if blood sugar still less than 80 mg/dl
5. If next meal is more than 1 hour away, eat a snack.

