Appendix VII for Adverse Event (AE) definitions and grading scale information.

If multiple toxicities are seen, the presence of a DLT should be based on the most severe toxicity experienced. Any patient who achieves a DLT will be taken off of glyburide immediately, but will still be evaluable.

Concerning Toxicity

1. Any **asymptomatic grade 3 or 4 hypoglycemia** as defined by CTCAE version 4.0.
2. Any **non-hematologic grade 3 or greater toxicity** (including neurologic toxicity) that is associated with a blood glucose level ≤ 80 mg/dl and is resolved with “low blood sugar intervention” (e.g. a return of blood glucose level to ≥ 80 mg/dl). **See Section 5.4.1.1 for a List of Low Blood Sugar Interventions.**

Serious Toxicity

1. Any **grade 5 toxicity** that is deemed by the investigator to be **at least possibly attributable to glyburide**.
2. Any **symptomatic grade 3 or 4 hypoglycemia associated with a non-hematologic grade 3 or greater toxicity** that is not resolved with “low blood sugar intervention” (e.g. does not

return to blood glucose level to ≥ 80 mg/dl) that is deemed by the investigator to be at least possibly attributable to glyburide. **See Section 5.4.1.1 for a List of Low Blood Sugar Interventions.**

Glyburide will be discontinued for any patient that meets the criteria for either a "**concerning toxicity**" or "**serious toxicity**". These patients will still be evaluable.

Any "**concerning toxicity**" that is observed in at least 6 (of 10 evaluable) patients will trigger a dose reduction (see section 7.1). After 1 dose reduction, if at least 6 (of 10 evaluable) patients are observed to have a "**concerning toxicity**", the study will be terminated.

Any "**serious toxicity**" that is observed in at least 1 (of 10 evaluable) patients will trigger a dose reduction. After 1 dose reduction, if at least 1 (of 10 evaluable) patients is observed to have a "**serious toxicity**", the study will be terminated.

5.3.1.1 If a dose reduction should occur, it will occur once the pre-specified DLT is reached.

Glyburide will be reduced to 0.75 mg po BID. In the event this dose reduction should occur, the Pilot Portion will be performed using the reduced dose (e.g. 10 evaluable patients are required to be assessed). If another DLT is observed at the reduced glyburide dose warranting a dose reduction, the study will be terminated.

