7.3.4 Grading Toxicities and Adverse Events

The descriptions and grading scales found in the revised NCI Common Terminology Criteria for Adverse Events (CTCAE) version 4.0 will be utilized for adverse event reporting on this study. The CTCAE version 4.0 is located on the CTEP website at http://ctep.cancer.gov/protocolDevelopment/electronic_applications/ctc.htm. See Appendix VII for Adverse Event (AE) definitions and grading scale information.

PILOT PORTION

If multiple toxicities are seen, the presence of a DLT should be based on the most severe toxicity experienced. Any patient who achieves a DLT will be taken off of glyburide immediately, but will still be evaluable.

Concerning Toxicity

1. Any asymptomatic grade 3 or 4 hypoglycemia as defined by CTCAE version 4.0.
2. Any non-hematologic grade 3 or greater toxicity (including neurologic toxicity) that is associated with a blood glucose level ≤ 80 mg/dl and is resolved with “low blood

sugar intervention" (e.g. a return of blood glucose level to ≥ 80 mg/dl). See **Section 5.4.1.1 for a List of Low Blood Sugar Interventions.**

Serious Toxicity

3. Any grade 5 toxicity that is deemed by the investigator to be at least possibly attributable to glyburide.
4. Any symptomatic grade 3 or 4 hypoglycemia associated with a non-hematologic grade 3 or greater toxicity that is not resolved with "low blood sugar intervention" (e.g. does not return to blood glucose level to ≥ 80 mg/dl) that is deemed by the investigator to be at least possibly attributable to glyburide. **See Section 5.4.1.1 for a List of Low Blood Sugar Interventions.**

Glyburide will be discontinued for any patient that meets the criteria for either a "**concerning toxicity**" or "**serious toxicity**". These patients will still be evaluable.

Any "**concerning toxicity**" that is observed in at least 6 (of 10 evaluable) patients will trigger a dose reduction (see section 7.1). After 1 dose reduction, if at least 6 (of 10 evaluable) patients are observed to have a "**concerning toxicity**", the study will be terminated.

Any "**serious toxicity**" that is observed in at least 1 (of 10 evaluable) patients will trigger a dose reduction. After 1 dose reduction, if at least 1 (of 10 evaluable) patients is observed to have a "**serious toxicity**", the study will be terminated.

RANDOMIZED PORTION

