APPENDIX II
GLUCOSE MONITORING INSTRUCTIONS

HOW OFTEN SHOULD I CHECK MY BLOOD SUGAR?

4 Times a Day (the study team will let you know if you can check less often than 4 times a day):

1. Before breakfast (fasting)
2. Before lunch
3. Before dinner
4. At bedtime

More Often:

- When you feel symptoms of low or high sugars, illness, or stress
- When your doctor changes your medicine doses
- If you are more physically active than usual
- If you are pregnant or planning to become pregnant

Please write the results down in your blood glucose log and take it to all your clinic visits.

Why Should I Check My Blood Sugar?

Knowing what your blood sugar is:

- Helps you make decisions about how to eat, exercise, or take my medicine
- Lets you and us know if my any treatment needs to be changed

What Should my Blood Sugar be?

Before Meals: 80-130

2 Hours After Meals: Less than 180

Bedtime: 90-150

Less than 80 is too low.

If the patient is having symptoms that they think are related to their blood sugar level or if their blood sugar level is below 80, they will be instructed to check their fingerstick blood glucose level again and begin to try the items listed in "**Low Blood Sugar Interventions**", described in **Section 5.4.1.1 and Appendix IV**. If "**Low Blood Sugar Interventions**" does not cause the blood sugar to rise above 80 after drinking or eating, or if their symptoms are not improving or worsening, the patient will be instructed to contact the study team and/or call 911 for emergency services.

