APPENDIX VII
CTCAE version 4.0 and Toxicity Criteria

This study will utilize **NCI Common Terminology Criteria for Adverse Events (CTCAE) version 4.0 for toxicity and Adverse Event Reporting**. A **grading** (severity) scale is provided for each Adverse Event (AE) term. A copy of the CTCAE version 4.0 can be downloaded from the CTEP web site at: http://ctep.cancer.gov/protocolDevelopment/electronic_applications/ctc.htm. All investigators and study staff have access to a copy of the CTCAE version 4.0. Also, see Sections 5.3 and 7.3 for additional information.

An **Adverse Event (AE)** is any unfavorable and unintended sign (including an abnormal laboratory finding), symptom, or disease temporally associated with the use of a medical treatment or procedure that may or may not be considered related to the medical treatment or procedure.

Grade refers to the severity of the AE. The CTCAE displays Grades 1 through 5 with unique clinical descriptions of severity for each AE based on this general guideline:

- **Grade 1:** *Mild; asymptomatic or mild symptoms; clinical or diagnostic observations only; intervention not indicated.*
- **Grade 2:** *Moderate; minimal, local or noninvasive intervention indicated; limiting age-appropriate instrumental Activities of Daily Living (ADL).*
- **Grade 3:** *Severe or medically significant but not immediately life-threatening; hospitalization or prolongation of hospitalization indicated; disabling; limiting self care Activities of Daily Living (ADL).*
- **Grade 4:** *Life-threatening consequences; urgent intervention indicated.*
- **Grade 5:** *Death related to AE.*

Adverse Event	GRADE				
	1	2	3	4	5
Hypoglycemia	<LLN – 55mg/dL; <LLN – 3.0 mmol/L	<55-40 mg/dL; <3.0-2.2 mmol/L	<40-30 mg/dL; <2.2-1.7 mmol/L	<30 mg/dL; <1.7 mmol/L; life-threatening consequences; seizures	Death

Definition: A disorder characterized by laboratory test results that indicate a low concentration of glucose in the blood.

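### An asymptomatic reading below 40 mg/dL is a DLT that requires an immediate stop, but in the visible text a patient whose glucose recovers is not told to report it, and no log review is scheduled before the week-1 post-SRS visit

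*Combined protocol and SAP*

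**What the plan says.** **The event and its consequence.** Item 1 of the concerning toxicities (5.3.1, 5.3.2, repeated in 7.3.4) is "Any asymptomatic grade 3 or 4 hypoglycemia as defined by CTCAE version 4.0". Appendix VII sets grade 3 at "<40-30 mg/dL; <2.2-1.7 mmol/L" and grade 4 below 30 mg/dL. Item 1 carries no condition about response to treatment. The consequence in the pilot (5.3.1) is "Any patient who achieves a DLT will be taken off of glyburide immediately, but will still be evaluable", and in the randomized part (5.3.2) "Any patient who achieves a DLT will be taken off of the investigational medication immediately, but will still be evaluable".

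**What the patient is told.** At 80 mg/dL or below, with or without symptoms, the patient takes carbohydrate, waits and rechecks (5.4.1, 5.4.1.1). Step 4 of that procedure reads "Repeat Steps 1-3 if blood sugar still less than 80 mg/dl". The contact rule in 5.4.1 applies when self-treatment "does not cause the blood sugar to rise above 80 mg/dl, or if symptoms persist, the patient will be instructed to contact the study team". Appendix II also requires contact if glucose does not rise above 80, and continues "if their symptoms are not improving or worsening, the patient will be instructed to contact the study team and/or call 911 for emergency services". Sections 5.4.1 and 5.4.2.2 add that a patient with a DLT must discontinue the drug.

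**When the team looks.** Log review and adverse event evaluation are first listed at week 1 post-SRS (4.1.6, 4.2.6, Appendix VIII). The day-of-SRS visit (4.1.5, 4.2.5) lists steroid documentation and continued self-testing only. Appendix II does tell the patient "Please write the results down in your blood glucose log and take it to all your clinic visits".

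**The concern.** One rule undercuts another. The protocol wants dosing to end as soon as an asymptomatic reading below 40 mg/dL occurs, but the contact rule depends on whether glucose recovers, not on how low it went. A patient who recovers has met the DLT definition and has no stated reason to call. The instruction to discontinue after a DLT helps only if someone recognizes the DLT, and the 40 mg/dL value appears in Appendix VII, outside the patient-education set (Appendices II-VI).

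What is at stake is a second low on continued dosing. Section 1.9 says that oral glyburide has not been shown to be safe in people without diabetes, and DLT occurrence is the pilot's primary endpoint (2.3.1), so prompt detection matters.

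**Working it through.** The plan states no figure for time to detection, so there is none to reproduce. Its pilot operating characteristics (9.5.1) are not in dispute. Exact binomial calculation with n = 10 gives 0.953 and 0.850 for the 6-of-10 rule (stated 95% and 85%), and 0.972 and 0.904 for the 1-of-10 rule (stated 97% and 90%).

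**Which readings escape the contact rule.** The reading must be below 40 mg/dL and asymptomatic, and must then rise above 80. The rise needed is more than 80 − 40 = 40 mg/dL. Some lows will not rise that far and will trigger a call. But step 4 of 5.4.1.1 allows repeat cycles without saying after which one to call, so a low that corrects on a later cycle may also go unreported. The persisting-symptoms clause cannot apply to an asymptomatic reading.

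**Inputs for the wait.**
- L, drug start to SRS: 5 to 9 days (4.1.4, 4.2.4).
- W, SRS to week-1 visit: 7 ± 3, so day 4 to 10 (4.1.6, 4.2.6).
- M, SRS to 1-month visit: 30, −5 or +10, so day 25 to 40 (4.1.7, Appendix VIII).
- Dosing: two tablets a day.

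**Event on the first day of dosing.** Wait = L + W.
- Nominal W: 5 + 7 = 12 to 9 + 7 = 16 days.
- With windows: 5 + 4 = 9 to 9 + 10 = 19 days.
- Doses in that time: at most 2 × 12 = 24 to 2 × 16 = 32 nominally, or 18 to 38 with windows. This slightly overcounts, because it includes any dose taken before the event.
- If the event were equally likely at any time before the week-1 visit (an assumption), the mean wait would be (L + W)/2 = 4.5 to 9.5 days.

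**Pilot event just after the week-1 visit.** Wait = M − W.
- Nominal: 30 − 7 = 23 days.
- With windows: 25 − 10 = 15 to 40 − 4 = 36 days.

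In the randomized part under 5.4.2.2, self-testing ends at week 1, so there is no later reading to report. The later wait arises there only if 5.4.2.3 applies and pilot-style testing continues.

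**Effect of a log review on the day of SRS.** A pre-SRS event then waits at most L = 5 to 9 days. An event just after SRS still waits W = 4 to 10 days. The longest wait before week 1 becomes max(5, 4) = 5 to max(9, 10) = 10 days. The wait after week 1 is unchanged; only a same-day call shortens that.

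**The case against.** The best defence is that week 1 is the protocol's chosen decision point. Sections 4.1.6.4 and 4.2.6.4 pair the adverse event evaluation with discontinuation, and 5.4.2.2 speaks of toxicities found at that visit. Immediate discontinuation can then be read as discontinuation once the event is identified. Concerning toxicity is also treated as less urgent than serious toxicity: other patients continue, and dose reduction needs 6 of 10 rather than 1 of 10. This reading is coherent, but it makes the stop rule only as fast as the next log review, and the patient can learn of the event on the day it occurs.

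Other points stand as limits. Patients bring logs to every visit, and Appendix VI invites calls about any concern, so some lows will surface earlier; neither instruction is tied to a value or a staff action. Five-fraction treatment (5.5, 6.4.1) may bring more attendances. The treatment schema, the consent pages and the Appendix IV figure are not visible, and in-person education is required, so the teaching actually given may be fuller. The 2.5 mg daily dose, entry glucose of at least 80 mg/dL and exclusion of patients unable to eat regular meals may make readings below 40 rare.

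A reader might infer that severe lows go untreated. They do not: self-treatment starts at 80 mg/dL. A reader might take 9-19 or 15-36 days as the usual delay. Those are maxima, and 36 pairs the earliest week-1 visit with the latest 1-month visit. A reader might also infer that DLTs drop out of the pilot count because of this gap. The documents do not support that, since the logs are reviewed at week 1 and collected at 1 month; the weakness shown is late action.

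**Conclusion.** The gap holds on the visible text. A patient can follow the stated contact rule after a corrected asymptomatic reading below 40 mg/dL and keep taking a drug that the protocol says must stop. The maximum unreviewed time is 12-16 days nominally for a first-day event (9-19 with windows) and, in the pilot, 23 days nominally for one just after week 1 (15-36 with windows).

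This rests on a lead of 5-9 days, on no unscheduled look at the log, and on the missing pages holding no lower reporting threshold. Sections 5.1 and 5.2 allow a longer lead; each extra day adds one day to the first figure. The number of patients affected cannot be estimated, because the documents give no rate of readings below 40 mg/dL. The point concerns safety procedure and leaves the sample size and stopping probabilities unchanged. It should be fixed because the remedy is cheap.

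**What to change.** 1. In 5.4.1, 5.4.2 and Appendices II and IV, add: *If any reading is below 40 mg/dL, even if it corrects and you feel well, do not take your next dose and call the study team the same day.* The team then applies the existing stop rule.
2. Mark the existing log-review row of Appendix VIII at the day-of-SRS visit, and list the review in 4.1.5 and 4.2.5.

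The first change closes the gap wherever patients are self-testing, including the pilot after week 1. The second is a backstop for patients who do not call.

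The cost is one sentence in the monitoring sections and handouts and one added item at a visit that already takes place. The downside is a few extra calls and an occasional dose held for a false low reading.

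No restart pathway is proposed, because the protocol has no criteria for confirming a reading after the fact. Sections 7.1.4 and 5.3.1 conflict on whether a patient with a DLT before SRS is evaluable; that is a separate matter to be settled on its own.

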APPENDIX IV
HOW TO MANAGE LOW BLOOD SUGAR

Low Blood Sugar Interventions

[figure not shown]
If you develop any of these symptoms during your time on study, please try:

- Drinking $\frac{1}{2}$ cup of juice or soda
- Eating a few pieces of candy
- Taking 3 or 4 glucose tablets

If it will be more than an hour until meal time, try eating a snack that is high in starch. Snacks that are high in starch include:

- Crackers
- Bread
- Cookies

Symptoms include:

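### The patient handout on low blood sugar (Appendix IV) gives 4 oz of soda where Section 5.4.1.1 requires 6 oz and adds candy with no amount; as a minor point, the rules at exactly 80 mg/dl disagree.

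*Combined protocol and SAP*

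**What the plan says.** Section 5.4.1.1 defines the intervention as 15 g of carbohydrate, taken as 3 or 4 glucose tablets, 4 oz of fruit juice (which it equates to half a cup), or "6 oz regular soda (about 1/2 can". A 15-minute rest, a recheck and a repeat rule follow. Section 5.4.1 describes when to use the intervention and directs the reader to the handout ("also see Appendix IV").

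The readable text of Appendix IV gives these options: 1/2 "cup of juice or soda"; "Eating a few pieces of candy"; and "Taking 3 or 4 glucose tablets".

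On thresholds, Section 5.4.1 states: "If fingerstick glucose levels reach ≤ 80 mg/dl (symptomatic or asymptomatic), the patient should begin" the intervention. The patient calls the study team or emergency services if treatment "does not cause the blood sugar to rise above 80 mg/dl, or if symptoms persist". Step 4 of Section 5.4.1.1 reads: "Repeat Steps 1-3 if blood sugar still less than 80 mg/dl". Appendix II starts the intervention for symptoms or for a value below 80, describes only values under 80 as too low, and sets the pre-meal target at 80 to 130. Its call-for-help rule, like that of Section 5.4.1, applies when glucose has not risen above 80.

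**The concern.** Patients in both portions receive Appendices II to VI and treat themselves at home. They are not on treatment for diabetes (Section 3.2.6). The protocol names hypoglycemia as the most common side effect of glyburide (Section 1.8) and says that safety of the oral form in non-diabetic people is unproven (Section 1.9). The sheet in the patient's hand should therefore carry the dose that the protocol specifies. A patient who follows the soda line takes less than that dose, and one who chooses candy cannot tell whether 15 g has been reached.

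The handout matters most late in the randomized portion. Under Section 5.4.2.2, patients without a toxicity at the one-week visit may stop fingersticks, while study drug continues to the one-month MRI. A low glucose would then be noticed mainly through symptoms, which is the situation Appendix IV addresses.

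The conflict at exactly 80 mg/dl matters less. A patient with that reading finds different instructions in documents meant to say the same thing. The value is plausible, since Section 3.1.8 accepts a screening glucose of 80.

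**Working it through.** **Soda.** All inputs come from Sections 5.4.1.1 and Appendix IV; no outside carbohydrate value is used.

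- Target dose: 15 g (5.4.1.1).
- Soda volume listed for that dose: 6 oz (5.4.1.1).
- Half a cup = 4 oz (from the juice line of 5.4.1.1).
- Soda volume in the handout: half a cup, so 4 oz (Appendix IV).

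Implied content of soda = 15 g / 6 oz = 2.5 g per oz. The protocol's own figure is recovered as 6 oz x 2.5 g/oz = 15 g. The handout gives 4 oz x 2.5 g/oz = 10 g. Shortfall = 15 - 10 = 5 g, and 5/15 = 33%.

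The same section implies 15 g / 4 oz = 3.75 g per oz for juice, so on the protocol's own scale one volume cannot serve for both drinks. Appendix IV uses one volume for both.

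**Option by option (readable text of Appendix IV against 5.4.1.1).**

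| Option | 5.4.1.1 | Appendix IV | Agreement |
|---|---|---|---|
| Juice | 4 oz | 1/2 cup = 4 oz | yes |
| Tablets | 3 or 4 | 3 or 4 | yes |
| Soda | 6 oz | 1/2 cup = 4 oz | no, about 10 g against 15 g |
| Candy | not listed | no count, weight or grams | no |

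Two of the four handout options differ.

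**A reading of exactly 80 mg/dl, without symptoms.**

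| Moment | Source | Rule | Result at 80 |
|---|---|---|---|
| First reading | Section 5.4.1 | start at 80 or below | treat |
| First reading | Appendix II | start below 80; pre-meal target 80 to 130 | no treatment, on target |
| Recheck | 5.4.1.1, step 4 | repeat if below 80 | repeat not called for |
| Recheck | 5.4.1 and Appendix II | call unless above 80 | call for help |

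Appendix II also differs from itself. Before treatment, 80 is on target; after treatment, failure to exceed 80 is a reason to call for help.

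**The case against.** The best defence is that little can come of this. An insufficient first dose of soda is caught by the recheck and repeat in Section 5.4.1.1 and by the call-for-help rule in Section 5.4.1 and Appendix II. The amounts are household measures. The conflict at 80 concerns a single meter value, well above the Appendix VII ranges for grade 2 (below 55) or grade 3 (below 40) hypoglycemia. Step 4 and the call rule can both be obeyed at 80: do not repeat, but call. All of this is fair and keeps the point minor. It does not make the soda line correct or give the candy an amount. At 80 it leaves a patient calling for help without being told to take a second dose.

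A reader might infer three stronger claims, which the documents do not support.

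- **That patients with a low reading but no symptoms go untreated, because the readable Appendix IV text starts from symptoms.** Appendix II belongs to the same handout set, starts below 80 without symptoms and points to Appendix IV. A figure in Appendix IV is also not reproduced in the text reviewed and could show a threshold. For the same reason, nothing can be concluded about whether that sheet shows the wait and recheck steps.
- **That 10 g falls below the lowest dose the protocol tolerates.** If four tablets make 15 g, three make 3 x 3.75 = 11.25 g. But no tablet strength is stated, so this floor is an assumption.
- **That the handout could change the pilot dose decision, since one serious toxicity in ten patients triggers a reduction.** By the hypoglycemia route, that needs symptomatic glucose below 40, a grade 3 or greater non-hematologic toxicity, failure to resolve, and attribution to glyburide. Any effect would be marginal, and the documents give no rate from which to estimate it.

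**Conclusion.** The point holds as a minor patient-safety correction. The Appendix IV soda line is wrong as written: 4 oz against 6 oz, or about 10 g against 15 g, a shortfall of one third. This rests only on the protocol's equating of 6 oz of soda with 15 g and of half a cup with 4 oz. The candy option has no counterpart in Section 5.4.1.1 and no amount. The instructions at exactly 80 mg/dl disagree across Section 5.4.1, step 4 and Appendix II, where the likely consequence is confusion.

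How often any of this would alter an episode cannot be estimated from the documents. Sample size and analysis are unaffected.

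**What to change.** In Appendix IV, give soda its own line at 6 oz (about half a can), with the word regular, which 5.4.1.1 has and the handout lacks. Delete candy, or state an amount equal to 15 g.

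For the threshold, keep the Section 5.4.1 rule, which is the more cautious one, and bring the rest into line with it. Change step 4 of 5.4.1.1 and the Appendix II trigger to 80 mg/dl or below, change the Appendix II statement of what is too low in the same way, and start its pre-meal target above 80. Start, repeat and call-for-help rules then agree. Lowering the Section 5.4.1 trigger to below 80 would remove the conflict at the first reading, but it gives up margin without a clinical argument.

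The toxicity definitions in Sections 5.3.1 and 5.3.2 can stay. They count a return to 80 or higher as resolved, but they classify events and do not tell patients when to treat. A patient at exactly 80 on recheck would repeat treatment while the event counts as resolved, which is harmless if noted.

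The cost is a wording amendment, reprinted handouts, and an occasional extra treatment at exactly 80.
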